APPENDIX 3. LIST OF EXCLUDED CONCOMITANT MEDICATIONS

The following medications are likely to influence evaluation of the safety, pharmacokinetics or efficacy of AGS-16C3F or axitinib, and will be strictly prohibited. If the investigator determines that any of the following medications are necessary to provide adequate medical support, the subject must be withdrawn from further study drug administration:

AGS-16C3F	Axitinib
Chemotherapy, radiotherapy, immunotherapy, monoclonal antibody therapy, or other medications intended for antitumor activity (i.e., other than AGS-16C3F) 
 • Note: Palliative radiation is permitted provided it does not interfere with subject safety and efficacy of the study drug being administered. Palliative radiation cannot be administered to any target lesion. 	Chemotherapy, radiotherapy, immunotherapy, monoclonal antibody therapy, or other medications intended for antitumor activity (i.e., other than axitinib) 
 • Note: Palliative radiation is permitted provided it does not interfere with subject safety and efficacy of the study drug being administered. Palliative radiation cannot be administered to any target lesion.
Investigational products or therapy other than AGS-16C3F	Investigational products or therapy Strong CYP3A4/5 inducers ¹

¹ *The drugs defined as CYP Substrates with Narrow Therapeutic Range by FDA's guidance - Guidance for Industry Drug Interaction Studies - Study Design, Data analysis, and Implications for Dosing and Labeling):*
<http://www.fda.gov/downloads/Drugs/GuidanceComplianceRegulatoryInformation/Guidances/UCM292362.pdf>

Examples of excluded inhibitors, inducers and substrates for enzymes and transporters are provided below. Subjects must have discontinued treatment with any of the following for at least 2 weeks prior to the first dose of study drug. This is not intended to be a comprehensive list. There could also be additional new drugs and marketed drugs that could be identified as inhibitors / inducers with continued research. Investigators will consult individual drug labels to determine liability of the drugs.

Strong CYP3A Inhibitors

boceprevir	nefazodone
clarithromycin	nelfinavir
conivaptan	posaconazole
grapefruit juice	ritonavir
indinavir	saquinavir
itraconazole	telaprevir
ketoconazole	telithromycin
lopinavir/ritonavir	voriconazole
mibefradil	

CYP3A4/5 Inducers

carbamazepine	rifapentin
dexamethasone	phenobarbital
rifabutin	phenytoin
rifampin	St. John's wort

Additional information for inhibitors/inducers/substrates of enzymes/transporters can be found in FDA's guidance (Guidance for Industry Drug Interaction Studies - Study Design, Data analysis, and Implications for Dosing and Labeling)¹ and from the Division of Clinical Pharmacology of Indiana University².

1. <http://www.fda.gov/downloads/Drugs/GuidanceComplianceRegulatoryInformation/Guidances/UCM292362.pdf>

2. <http://medicine.iupui.edu/clinpharm/ddis/main-table/>

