**5.1.3.2 Prohibited Concomitant Medications**

The investigator may prescribe any medication necessary to ensure the safety and wellbeing of the subject during the study. Please refer to Appendix 12.1 for additional information.

Protocol prohibited medications that are needed temporarily to treat an AE are permitted (e.g., dexamethasone used to treat nausea).

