**Table 7 Prohibited Medications for Subjects Randomized to Axitinib**

	Prohibited Medication	Reason to Exclude
1	Chemotherapy, radiotherapy, immunotherapy, monoclonal antibody therapy or other medications intended for antitumor activity other than axitinib 	Likely affect efficacy, safety or pharmacokinetics of AGS-16C3F
2	Investigational products or therapy	
3	Strong CYP3A4/5 inducers (e.g., rifampin, dexamethasone, phenytoin, carbamazepine, rifabutin, rifapentin, phenobarbital, and St. John's wort) 	Axitinib is a substrate of CYP3A4/5

 Palliative radiation is permitted provided it does not interfere with subject safety and efficacy of the study drug being administered. Palliative radiation cannot be administered to any target lesion. Medications used to treat bone metastases (e.g., zoledronic acid, denosumab, etc.) are allowed provided they are not initiated at the same time as Cycle 1 Day 1.

 The drugs defined as CYP Substrates with Narrow Therapeutic Range by FDA's guidance - Guidance for Industry Drug Interaction Studies - Study Design, Data analysis, and Implications for Dosing and Labeling): <http://www.fda.gov/downloads/Drugs/GuidanceComplianceRegulatoryInformation/Guidances/UCM292362.pdf>

The use of the following medications and foods should be avoided or used with caution and closely monitored:

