5. ANALYSIS SETS

The sponsor will make decisions about subject exclusions from analyses and authorize/approve the analysis set membership prior to each reporting event. Membership in all analysis sets will be determined prior to the Main Analysis, based on all data available at that time. Analysis sets will be updated if appropriate at the time of the End of Study Analysis, and any changes between the Main Analysis and the End of Study Analysis sets will be documented.

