5.2. PER PROTOCOL ANALYSIS SET [PPS]

The per-protocol analysis set (PPS) will consist of all subjects in the FAS who did not experience protocol deviations that might affect the efficacy endpoints. Important protocol deviations that might affect efficacy are defined separately for each version of the protocol, as the inclusion/exclusion numbering may change between versions. Specifically, subjects are expected to be excluded from the PPS due to the following reasons:

- PD1 - Did not meet the inclusion/exclusion criteria that are prognostic of the efficacy endpoints; i.e., one or more of:
 - Original Protocol, Amendment 1, Amendment 2, or Amendment 3: Inclusion Criteria 3, 4, 5, 7, 9, 10 or Exclusion Criteria 1, 2, 3, 4, 5, 6, 8, 9, 10, 11, 12, 14.
- PD2 Developed withdrawal criteria during the study and was not withdrawn.
- PD3 - Received wrong treatment or incorrect dose
 - Did not receive treatment
 - Not treated as assigned (i.e., received the wrong drug)
- PD4 – Received excluded concomitant treatment
 - Prohibited concomitant medication [see SAP Appendix 3]
 - Prohibited non-drug therapy [see SAP Appendix 3]

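### The per-protocol exclusion for prohibited medication rests on SAP Appendix 3, which omits the protocol's exception for temporary use to treat an adverse event; read literally, this could remove protocol-compliant subjects from the axitinib arm only

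*SAP*

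**What the plan says.** SAP 5.2 builds the PPS from the FAS by removing subjects with deviations that might affect efficacy. It says that "subjects are expected to be excluded from the PPS due to the following reasons" and lists PD1 to PD4. Under PD4, excluded concomitant treatment, the drug item reads "Prohibited concomitant medication [see SAP Appendix 3".

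SAP Appendix 3 describes its medications as "likely to influence evaluation of the safety, pharmacokinetics or efficacy of AGS-16C3F or axitinib, and will be strictly prohibited". Both columns bar "Chemotherapy, radiotherapy, immunotherapy, monoclonal antibody therapy, or other medications intended for antitumor activity", with a note that excepts palliative radiation. Only the axitinib column adds "Strong CYP3A4/5 inducers". Dexamethasone stands in the list of CYP3A4/5 inducers below the table.

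Protocol 5.1.3.2 says: "Protocol prohibited medications that are needed temporarily to treat an AE are permitted (e.g., dexamethasone used to treat nausea". The synopsis has the same exception, at the investigator's discretion. Protocol Appendix 12.1, the counterpart of SAP Appendix 3, has it too. Protocol Tables 6 and 7 and Appendix 12.1 also say that bone-metastasis drugs such as zoledronic acid or denosumab "are allowed provided they are not initiated at the same time as Cycle 1 Day 1". SAP Appendix 3 carries neither provision.

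**The concern.** A per-protocol set should be defined by the protocol's own idea of compliance. Here the list that decides PD4 is stricter than the protocol, and the SAP's log of changes from protocol (Section 3.3) does not record the difference as a choice.

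The gap need not fall evenly on the arms. The inducer ban is in the axitinib column alone, so temporary dexamethasone can trigger PD4 in that arm and not in the other. The trigger is treatment of an adverse event after randomization, which may be related to time on treatment and so to PFS. The PPS is used to check the primary PFS result and is also analysed for every secondary efficacy endpoint. An exclusion of this kind can move the hazard ratio in the set meant to show that the FAS result is robust.

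**Working it through.** **1. Texts side by side**

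| Question | Protocol v6.0 | SAP Appendix 3 |
|---|---|---|
| Strong CYP3A4/5 inducers barred for | Axitinib only (Table 7, Appendix 12.1) | Axitinib only |
| Dexamethasone | Named as a strong inducer in Table 7 | In the inducer list, not labelled strong |
| Temporary use to treat an AE | Permitted (synopsis, 5.1.3.2, Appendix 12.1) | Not mentioned |
| Bone-metastasis drugs | Allowed unless started with Cycle 1 Day 1 | Not mentioned |
| Two-week washout before first dose | Both arms | Both arms |

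The arms therefore differ only for on-treatment use. An axitinib subject given brief dexamethasone for nausea complies with the protocol but meets PD4 if Appendix 3 is applied as written and Table 7's classification is used. An AGS-16C3F subject with the same use does not meet PD4.

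**2. The plan's design figures**

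With HR = 4/6, one-sided alpha 0.1 and 80% power, the Schoenfeld formula gives 4 × (1.2816 + 0.8416)² / (ln 0.667)² ≈ 110 events, with power 0.801. The boundary is exp(−2 × 1.2816/√110) = 0.783. These match SAP 3.5. They belong to the FAS analysis and do not change.

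**3. How many subjects (illustration)**

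- Axitinib arm: 134/2 = 67.
- Nausea on axitinib: 33% (Protocol 1.3.2, pooled data on 672 patients), so 67 × 0.33 ≈ 22.
- Assumption, with no source in the documents: 10% to 30% of these receive short dexamethasone. That gives 22 × 0.10 to 22 × 0.30, or about 2 to 7 subjects (3% to 10% of the arm).
- Nausea in phase 1 at the AGS-16C3F study dose was 69% of 13 subjects (Protocol 1.3.1.2 and 1.4). The arm that may have more nausea would lose nobody under this item.

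**4. What such a loss could do to the PPS (illustration)**

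Start from 55 events per arm and drop a share p of axitinib subjects only.

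(a) Dropping unrelated to PFS. Events are 55 + 55(1 − p), and only precision suffers.

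(b) A subject is dropped if dexamethasone starts before the PFS event, with a constant start rate d and exponential PFS with hazard λ. Then p = d/(λ + d). Retained axitinib subjects have hazard λ + d = λ/(1 − p), so the PPS hazard ratio is the true one times (1 − p).

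| p | Dropped of 67 | PPS events | (a) Power at HR 0.667 | (b) PPS HR if no true effect | (b) Chance of one-sided p < 0.1 if no true effect |
|---|---|---|---|---|---|
| 5% | about 3 | 107 | 79.3% | 0.95 | about 16% |
| 10% | about 7 | 105 | 78.5% | 0.90 | about 23% |
| 20% | about 13 | 99 | 76.5% | 0.80 | about 43% |

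Simulation of (b) gave retained axitinib medians of 3.6 months at 10% and 3.2 months at 20%, against 4.0. The 20% row would need about 13 of the 22 nauseated subjects (roughly 60%) to be treated this way, so it is an outer case.

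**The case against.** The best answer is that SAP 5.2 does not remove these subjects at all. Its governing sentence concerns protocol deviations, SAP Section 10 defines the important ones through Protocol 7.7 and 8.1.6, and use that the protocol permits is not a deviation. Exclusion is described as expected, not automatic. SAP Section 5 adds that "The sponsor will make decisions about subject exclusions from analyses" and approves membership before each reporting event. The label of strong inducer for dexamethasone comes from Protocol Table 7, which sits under the same Section 5.1.3.2 that holds the exception.

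Much of this stands. A reader might infer that compliant subjects will certainly be dropped; the documents support only that they could be. What remains is that PD4 points to Appendix 3 by name, and no written rule restores the exception. Leaving it to case-by-case sponsor decisions in an open-label trial is weaker than a rule fixed beforehand.

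A reader might also infer that the SAP bans bone-metastasis drugs. It does not name them. Denosumab is caught only if the antibody wording is detached from antitumor intent, and zoledronic acid only if it is judged antitumor. Any effect would fall on both arms, so this is minor.

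Nor is the asymmetry an SAP invention: the protocol itself bars inducers for axitinib only. It becomes a problem when the exception is lost.

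Finally, the SAP rests on protocol v4.0, which is not supplied, so whether the exceptions were already there cannot be checked. The Amendment 5 summary does not list them as new. The current texts disagree in either case.

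**Conclusion.** The SAP is wrong as written on a narrow point: the list that defines PD4 lacks an exception that the protocol states in three places. Under a literal reading, with Table 7's classification of dexamethasone, a protocol-compliant axitinib subject would leave the PPS and an AGS-16C3F subject with the same use would stay.

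The size is unknown. The 2 to 7 subjects rest on an assumed rate of use. The hazard-ratio shift rests further on a constant start rate and exponential PFS. Under that model the PPS tilts towards AGS-16C3F. If dexamethasone marks sicker subjects with shorter PFS, the shift would be smaller or could reverse, so the documents do not settle its direction.

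A reader might infer that the trial's main result is at risk. It is not. The primary analysis is in the FAS, and the PPS is one of several checks, alongside Censoring Rules Sets 2 to 4, the unstratified model and central-review PFS. The change is worth making because it is cheap and the PPS should measure compliance with the protocol actually in force.

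**What to change.** Reconcile SAP Appendix 3 with Section 5.1.3.2 and Appendix 12.1 of the current protocol. Add one sentence to SAP 5.2: concomitant use permitted by Protocol 5.1.3.2 or Appendix 12.1, including the bone-medication allowance, is not PD4.

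Pointing PD4 to Protocol Tables 6 and 7 alone would not be enough. Table 7 lists dexamethasone, and the temporary-use exception stands in the opening text of 5.1.3.2 and in Appendix 12.1. While aligning the texts, settle one further difference: Tables 6 and 7 and SAP Appendix 3 mention monoclonal antibody therapy in the antitumor item, and Protocol Appendix 12.1 does not.

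If the stricter rule is intended for the PPS, record and justify it in the SAP's log of changes. Either way, do it before PPS classification. The cost is SAP text, with no new data and no change to sample size. Which medication rule is clinically right is not judged here.
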